#### Exploratory Endpoint for Phase I (Optional Imaging Sub-study):

- Maximum Standardized Uptake Value (SUVmax) of C-Glutamine and F-FSPG uptake at pre-treatment and after one cycle of treatment.

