#### **4.5. Optional Imaging Sub-Study for Phase I (Maximum of 9 patients)**

Patients accrued to the Phase I Dose Escalation portion of this study may optionally participate in an imaging sub-study. Patients must sign the optional consent for participation in this sub-study and be willing to undergo four research PET imaging techniques (C-Glutamine and F-FSPG), two pre-treatment and two after one cycle of treatment. Please refer to Table 6.1 for details regarding the timing of relevant assessments.

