## 6. SCHEDULE OF ASSESSMENTS

### 6.1. Study Calendar

Protocol Activities 1 Cycle = 4 weeks (28 days)	Screening (Day -14 to Day -1)	CYCLE 1			CYCLES ≥ 2		Post-Treatment	
		Day 1	Day 15	Day 28 	Day 1 (± 1 day) 	Day 15 (± 1 day) 	EOT (≤ 14d after last treatment) 	Follow-Up (28d + 7d after last study dose) 
Assessments & Observations								
Consent, Baseline Characteristics & Eligibility 	X							
Physical and Skin Examination 	X	X 	X		X	X	X	X
ECOG Performance Status	X	X	X		X	X	X	X
Vital Signs	X	X	X		X	X	X	X
Height	X							
Weight 	X	X 	X		X	X	X	X
Review of Con Meds and Adverse Events 	X	X	X		X	X	X	X
Study Drug Compliance (Dosing Diary)			X	X	X		X	
DLT Evaluation (dose-escalation only) 		X	X	X	X			
Laboratory Assessments								
Hematology and Blood Chemistry 	X	X 	X		X	X	X	X
Urinalysis	X							
Pregnancy Test 	X	X		X			X	
Disease Assessments								
CT or MRI Scan 	X				X		X 	X 
 C-Glutamine PET/CT (Optional in Phase I only, not performed in Phase II) 	X 			X 				
 F-FSPG PET/CT (Optional in Phase I) 	X 			X 				
Survival Follow-Up								X 
Biospecimen Collections								
Research Tumor Biopsy (Phase II Only)	X							
Pharmacokinetic (PK) Blood (Optional in Phase I) 	X			X				
Pharmacodynamic (PD) Blood (Phase II Only) 		X		X			X	
Treatment								
CB-839 oral administration 		Continuous oral twice daily dosing 						
Panitumumab infusion 		X	X		X	X		
Irinotecan infusion (Phase I Only) 		X	X		X	X		

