All patients in Phase II will undergo two  $^{18}F$ -FSPG imaging sessions at baseline and just prior to cycle 2 of therapy. Our preliminary data suggest that the  $^{18}F$ -FSPG  $SUV_{max}$  (predictor) has a standard deviation of 2.04 (95% CI 1.42 to 3.58). From previous clinical trial data, the median (range) and mean (standard deviation) of the change in the sum of index lesions from patients treated with EGFR mAb therapy were 4.9 mm (-24 mm to 42 mm) and 6 mm (15.8 mm), respectively. Using the standard deviations (SDs) and their 95% confidence intervals for PET  $SUV_{max}$  (predictor) and change in tumor size, table 11 lists the true slope estimates that provide 80% power to reject the null hypothesis of no association between  $^{18}F$ -FSPG imaging and tumor response. From the estimated SDs for PET  $SUV_{max}$  and change in tumor size, a reformulation of the coefficient of determination ( $R^2$ ) gives the correlation associated with the slope estimates

$$r = \sqrt{\frac{1}{(\sigma/B \cdot SX)^2 + 1}}$$

where  $\sigma$  is the SD of the residuals,  $B$  is the slope and  $SX$  is the standard deviation for PET  $SUV_{max}$ .

The estimated correlations for the scenarios in table 11 have a mean ( $\pm$  standard deviation) of  $0.475 \pm 0.0002$ , which represent biologically and clinically meaningful associations between early changes in PET  $SUV_{max}$  and tumor size.

Because  $^{11}C$ -Glutamine is a novel tracer, we will use the same power and sample size analyses as  $^{18}F$ -FSPG.

Table 12. True slope estimates required to achieve 80% power to reject the null hypothesis of no association between baseline PET  $SUV_{max}$  and change in the sum of index lesions.

SD for $^{18}F$ -FSPG $SUV_{max}$	SD for Change in Tumor Size at Best Response		
	12	16	24
1.42	4.01	5.35	8.03
2	2.85	3.80	5.70

[figure not shown]
3.58	1.59	2.12	3.18
------	------	------	------

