A similar linear regression will be conducted to predict change in tumor size by the change in PET  $SUV_{max}$  measured just prior to cycle 2. Using a standard deviation of 2 from table 11, we can estimate the SD of the difference in PET  $SUV_{max}$  as  $\sqrt{2V(1-r)}$  where  $V$  is the assumed common variance (for a single SD of 2, the  $V=4$ ) of the two measurements and  $r$  is the correlation between them. For a correlation set of 0.3, 0.5, and 0.7, the SD's of the difference in PET  $SUV_{max}$  are 2.36, 2, and 1.54. The data in table 12 reflect an average (SD) correlation between change in tumor size and  $\Delta SUV_{max}$  of  $0.475 \pm 0.0003$ .

Table 13. True slope estimates required to achieve 80% power to reject the null hypothesis of no association between change in PET $SUV_{max}$ just prior to cycle 2 and change in the sum of index lesions.			
SD for $^{18}F$ -FSPG $SUV_{max}$	SD for Change in Tumor Size at Best Response		
	12	16	24
1.54	3.70	4.93	7.4
2	2.85	3.80	5.70
2.37	2.40	3.21	4.81

Time-to-event. We expect median progression-free and overall survival of approximately 1.9 and 6.4 months, respectively. Power to reject a  $HR=1$  for a single predictor in the Cox regression model depends on the number of events (progressions or deaths), the variability of the predictor, and the true HR [14]. Assuming exponential survival, we estimate that 29 and 21 patients will have progressed or expired by 12 months among the 29 patients in the phase I/II trial. We will use Cox proportional hazards model to estimate the association between PET  $SUV_{max}$  and PFS and OS. Preliminary data suggest  $^{18}F$ -FSPG  $SUV_{max}$  has a standard deviation of 2.04 (95% CI 1.42 to 3.58). Figure 4 illustrates the hazard ratios necessary to reject the null hypothesis that  $HR=1$  versus the alternative that the  $HR \neq 1$  assuming SD estimates for PET  $SUV_{max}$ , a type I error of 5% and 80% or 90% power. For PFS and OS, we expect to have at least 90% power to reject the null hypothesis that the  $HR=1$  if the for a SD PET  $SUV_{max}$  of 1.54 and the true hazard ratios are 1.65 and 1.53 or larger, respectively.

**Figure 5:** True hazard ratios (HRs) scenarios necessary to reject ( $p<0.05$ ) a null hypothesis with 80% and 90% power.

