### Power Analysis:

PFS/OS. Estimated median PFS and OS in this patient population is 1.9 and 6.4 months, respectively, with an estimated 29 and 21 patients progressing or expired by 12 months. In preliminary data, the average standard deviation (SD) and bootstrapped (1000 replications) 95% confidence intervals of the SD for the deltaCt values of 84 genes was 2 cycles (1.85 to 2.14 cycles). Twenty-nine patients provide at least 90% power to reject the null hypothesis that the HR=1, assuming the qRT-PCR SD is 2 for true hazard ratios are 1.35 and 1.42 or larger, respectively.

**Figure 6:** True hazard ratios (HRs) scenarios necessary to reject ( $p<0.05$ ) a null hypothesis with 80% and 90% power.

Change in Tumor Size. Among 20 patients treated with mAb therapy, the mean SD of the change in the sum of index lesions was 6 mm (15.8 mm). Using the SD and their 95% confidence intervals for qRT-PCR (predictor; data provided above) and change in tumor size among 29 patients, table 2 lists the true slope estimates that provide 80% power to reject the null hypothesis of no association between qRT-PCR and tumor response. Given our preliminary data, 29 patients provide 80% power to detect ( $p<0.05$ ) a 3.8 mm change in tumor volume per deltaCt cycle.

Table 14. True slope estimates (mm/cycle) required to achieve 80% power to reject the null hypothesis of no association between baseline qRT-PCR and change in the sum of index lesions.

SD for qRT-PCR	SD for Change in Tumor Size at Best Response		
	12	16	24
1.85	3.08	4.11	6.16

2	2.85	3.80	5.70
2.14	2.66	3.55	5.33

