Patients from this protocol will also provide tissue for modelling individual gene expression (e.g., log(FPKM) using RNA-seq. Following extensive processing and quality control, we will model individual gene expression (e.g., log(FPKM) separately against  $^{11}\text{C}$ -Glutamine and  $^{18}\text{F}$ -FSPG PET as continuous dependent variables with standard linear regression with a FDR selection criteria of 5%. This gene signature will be confirmed using feature selection via the elastic net with 4-fold cross validation. This gene signature will be further annotated using knowledge base pathway analysis. Due to the relatively smaller sample size, we will further summarize the gene signature by generating a compound score based on the univariate regression analysis considering one gene at a time on change in tumor size (pFDR < 0.05) as a cutoff point for selection of important features. For the  $i^{\text{th}}$  patient, the compound score (prediction index) for the gene signature is:

$$c_i = \sum_{j=1}^k (\text{sign of } \beta_j) w_j x_{j,i} .^{52}$$

Here  $w_j$  is the Wald statistic and  $\beta_j$  is the coefficient from linear regression analysis for the set of  $j=1$  to  $k$  selected significant features. These summary prediction indices will again be used to predict change in tumor size. For that analysis, we will determine the statistical significance of the compound score using a permutation test (10,000 permutations). Further, we will carry out the same method using the Cox (proportional hazards) regression model (i.e.,  $h_i(t) = h_0(t) \exp(\psi c_i)$ ) for PFS. Finally, we will conduct internal validation and model calibration using Efron's optimism bootstrap ( $b=500$ ). Standard goodness-of-fit parameters (e.g. coefficient of determination) will be adjusted for over-optimism and predicted values adjusted to evaluate calibration plots that elucidate the predictive power of the gene expression model in future datasets.

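### Section 15 prints the SUVmax hazard ratios for PFS and OS in the wrong order, and extends 29-patient power to 11C-glutamine PET, which at most 9 patients can receive

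*Combined protocol and SAP*

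**What the plan says.** **Hazard ratios.** The time-to-event paragraph of Section 15 says that Cox power depends on the number of events, the spread of the predictor and the true hazard ratio. From exponential medians of 1.9 months (PFS) and 6.4 months (OS) it expects 29 progressions and 21 deaths by 12 months among 29 patients. It says that 18F-FSPG SUVmax "has a standard deviation of 2.04 (95% CI 1.42 to 3.58"). It then claims at least 90% power, for PFS and OS in that order, with an SD "of 1.54 and the true hazard ratios are 1.65 and 1.53 or larger, respectively". The gene-expression power analysis later in Section 15 uses the same event counts and also claims at least 90% power, "assuming the qRT-PCR SD is 2 for true hazard ratios are 1.35 and 1.42 or larger", again PFS first.

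**11C-glutamine.** After the 18F-FSPG slope calculations, Section 15 says that 11C-glutamine "is a novel tracer, we will use the same power and sample size analyses as" 18F-FSPG. For RNA-seq it says "we will model individual gene expression (e.g., log(FPKM) separately against" 11C-glutamine and 18F-FSPG uptake. Other sections restrict that tracer:
- Section 4.5 is headed "Optional Imaging Sub-Study for Phase I (Maximum of 9 patients").
- Section 3.2 lists 11C-glutamine SUVmax only under "Exploratory Endpoint for Phase I (Optional Imaging Sub-study").
- The calendar in Section 6.1 labels the scan "Optional in Phase I only, not performed in Phase II", and marks the research tumor biopsy as Phase II only.
- Section 4.1, criterion 7, asks expansion patients for two 18F-FSPG scans.

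Other text disagrees with these. The synopsis inclusion criteria ask expansion patients for four scans covering both tracers, Sections 2.6.2 and 7.12 speak of about 15 patients, and Table 1 in Section 7.12.1 lists 29.

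**The concern.** With the predictor, error rate and power held fixed, the detectable log hazard ratio falls as one over the square root of the number of events. PFS has more events than OS, so its detectable hazard ratio must be the smaller. The SUVmax sentence has it the other way round, while the qRT-PCR sentence, built on the same events, has the expected order.

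The SD in the sentence is also unclear. The value 1.54 is the plan's SD for the *change* in SUVmax when the two measurements correlate at 0.7. The surrounding text gives the *baseline* SD, so the reader cannot tell which predictor is meant.

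For 11C-glutamine, the power calculation being borrowed rests on 29 Phase II patients, none of whom has that scan under the calendar.

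At stake are an OS power claim that does not hold at the SD it names, a power claim for a sub-study less than a third the size assumed, and one pre-specified gene-by-tracer model with nothing to fit.

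**Working it through.** **1. Events.** Medians, 12 months and 29 patients are from Section 15.
- PFS: 29 × (1 − 0.5^(12/1.9)) = 28.6, printed as 29.
- OS: 29 × (1 − 0.5^(12/6.4)) = 21.1, printed as 21.

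Both reproduce.

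**2. Method.** For a Cox model with one continuous predictor and a two-sided 5% test:
- detectable HR at 90% power = exp[(1.960 + 1.2816) / (SD × √D)]
- power = Φ(SD × √D × ln HR − 1.960)

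where D is the number of events.

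**3. Reproducing the qRT-PCR pair (SD 2).**
- PFS: exp[3.2416 / (2 × √29)] = 1.351
- OS: exp[3.2416 / (2 × √21)] = 1.424

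The plan prints 1.35 and 1.42, so this formula matches the plan's own figures.

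**4. The SUVmax pair.** Hazard ratios detectable with 90% power:

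| SD | PFS (29 events) | OS (21 events) |
|---|---|---|
| 1.42 | 1.528 | 1.646 |
| 1.54 | 1.478 | 1.583 |
| 2.04 | 1.343 | 1.414 |

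The printed order, 1.65 then 1.53, is not reproduced at SD 1.42, 1.54, 2, 2.04, 2.36 or 3.58, with a one- or two-sided test, at 80% or 90% power. The two values do match SD 1.42, the lower confidence limit of the baseline SD, in reverse order.

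Power at SD 1.54:

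| | PFS | OS |
|---|---|---|
| As printed | HR 1.65: 98.6% | HR 1.53: 85.1% |
| Swapped | HR 1.53: 94.1% | HR 1.65: 94.2% |

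For example, OS as printed is Φ(1.54 × √21 × ln 1.53 − 1.960) = 85.1%.

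**5. Dependence on the SD.** OS at HR 1.53 reaches 90% power when SD = 3.2415 / (√21 × ln 1.53) = 1.663. Power is 79.0% at SD 1.42 and 97.8% at SD 2.04.

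**6. Where 1.54 comes from.** The plan's SD of a difference is √(2V(1 − r)) with V = 4. At r = 0.7 this is √(8 × 0.3) = 1.549, printed as 1.54.

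**7. 11C-glutamine.** The slope tables correspond to a correlation of slope × SD of SUVmax / SD of tumor change. For example, 3.80 × 2 / 16 = 0.475. A noncentral t with noncentrality √n × r / √(1 − r²) gives 80.0% power at n = 29, so the 18F-FSPG figure reproduces. At the same correlation:

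| n | Noncentral t | Simulation, random SUVmax | Fisher z |
|---|---|---|---|
| 29 | 80.0% | 76.4% | 75.0% |
| 15 | 49.0% | 45.6% | 43.2% |
| 9 | 28.9% | 26.1% | 24.4% |

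With 9 patients, 80% power needs r of 0.74 (noncentral t) to 0.82 (Fisher z). An observed r of 0.475 would have a Fisher 95% interval of −0.28 to 0.87.

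**8. RNA-seq against 11C-glutamine.** The calendar puts the scan in Phase I only and the research biopsy in Phase II only. No patient has both.

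**The case against.** - **Only the OS half fails.** The PFS half is true as printed, and the OS shortfall is about 5 points at an SD that is not the plan's best estimate. At 2.04 the OS claim holds with room to spare. This is right and limits the error, but the sentence names 1.54 and is false there.
- **More deaths may accrue than 21.** Survival follow-up runs for up to a year after last treatment. At 14 months, 29 × (1 − 0.5^(14/6.4)) = 22.6 deaths, and OS power at SD 1.54 is about 88%. The gap narrows but does not close.
- **The fault may be the SD label as well as the order.** The match at SD 1.42 suggests so. It remains an inference, because the hazard-ratio figure is not available in the text reviewed and may show the correct values. A swap alone makes the sentence true but leaves the SD question open.
- **The plan never claims 80% power for 9 patients, and 0.475 was derived for 18F-FSPG.** True. The conflict appears only when the power sentence is read with Section 4.5 and the calendar. But adopting the same power and sample-size analysis for this tracer can only mean that correlation and 29 patients.
- **Other tissue might be used for RNA-seq.** Section 5.1 lists a tissue block form at enrollment. The plan does not say that such tissue feeds this analysis, so the point stands for the research biopsy it does describe.
- **No decision rule depends on either statement.** Agreed. The Cox estimates and intervals will be the same whatever the power text says.

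**Conclusion.** Both power statements are wrong as written.

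The SUVmax hazard ratios are in the wrong order for 29 PFS events and 21 deaths. At the stated SD of 1.54, OS power at 1.53 is 85.1% rather than at least 90%, and the claim fails at any SD below about 1.66. This assumes the single-covariate Cox formula, which reproduces the plan's qRT-PCR pair, and the plan's own event counts.

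The 29-patient power does not carry over to 11C-glutamine. With the 9 patients that Section 4.5 allows, power at a correlation of 0.475 is about 24–29%. Even with the 15 mentioned in Sections 2.6.2 and 7.12 it is about 43–49%. The RNA-seq model against that tracer has no patients under the calendar, while the 18F-FSPG model can still be run.

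The effect is confined to secondary (18F-FSPG against OS) and exploratory (11C-glutamine) analyses. The primary response-rate test, the 29-patient sample size and the 18F-FSPG slope tables stand.

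**What to change.** **Hazard-ratio sentence.** At minimum, print 1.53 for PFS and 1.65 for OS. That is true at SD 1.54, and those values are the 90% thresholds at SD 1.42. Better, print the thresholds for SD 1.54: 1.48 for PFS and 1.59 for OS (the exact OS value is 1.583; 1.58 gives 89.8% and 1.59 gives 90.5%). Either way, name the SD, say whether the predictor is baseline SUVmax or its change, and add the values at the estimated baseline SD of 2.04 (1.343 and 1.414). Check the hazard-ratio figure against the corrected text.

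**11C-glutamine.** Delete the sentence that borrows the 18F-FSPG power analysis. Report the sub-study descriptively, with up to 9 patients and estimates with 95% intervals. Take 11C-glutamine out of the RNA-seq model and keep 18F-FSPG.

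**Consistency.** Reconcile the scan requirement in the synopsis and the counts in Sections 2.6.2, 7.12 and Table 1 with Section 4.1 criterion 7, Section 4.5 and the calendar. If the sponsor intends a number other than 9, Section 4.5 must say so and the precision must be restated for it.

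**Cost.** Text changes only, with no added patients, scans or procedures and no change to the primary design. The synopsis change touches eligibility text, so it goes through the amendment process in Section 14.2. The stated detectable OS hazard ratio becomes less favorable, and the 11C-glutamine power claim is given up.

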#### Pharmacokinetic Modeling.

The  $^{18}\text{F}$ -FSPG PET/CT data will be analyzed using pharmacokinetic modeling. Three-dimensional regions of interest will be manually drawn using ASIPro software over tumor and the abdominal aorta (to estimate the arterial input function, [AIF]) of dynamically acquired PET images. Venous samples will be collected over the course of scanning to measure  $^{18}\text{F}$ -FSPG plasma concentrations, confirm blood pool radioactivity, evaluate metabolism, and to calibrate image-derived input functions. We will utilize the PMOD software package to assist in the estimation of various model parameters (e.g., influx ( $K_1$ ), efflux ( $k_2$ )) in order to calculate tracer flux:

$$K_{\text{flux}} = (K_1 * k_3) / (k_2 + k_3).$$

[figure not shown]
All pharmacokinetic modeling endpoints are focused on estimation; thus, no formal hypothesis testing will be performed. All point estimates of outcome measures will be accompanied by 95% (e.g. based on standard Gaussian methods or bootstrap methods, as appropriate) confidence intervals. Categorical variables will be summarized in frequency tables. Continuous variables will be summarized using the minimum, 25th, 50th, and 75th percentiles and the maximum value.

### Gene expression signatures

Patients from this protocol will provide pre-treatment tissue for collection of tumor RNA and qRT-PCR analysis of genes that regulate intracellular Gln metabolism. We hypothesize that qRT-PCR based gene expression is associated with change in tumor size, progression-free (PFS) and overall survival (OS).

### Power Analysis:

PFS/OS. Estimated median PFS and OS in this patient population is 1.9 and 6.4 months, respectively, with an estimated 29 and 21 patients progressing or expired by 12 months. In preliminary data, the average standard deviation (SD) and bootstrapped (1000 replications) 95% confidence intervals of the SD for the deltaCt values of 84 genes was 2 cycles (1.85 to 2.14 cycles). Twenty-nine patients provide at least 90% power to reject the null hypothesis that the HR=1, assuming the qRT-PCR SD is 2 for true hazard ratios are 1.35 and 1.42 or larger, respectively.

**Figure 6:** True hazard ratios (HRs) scenarios necessary to reject ( $p<0.05$ ) a null hypothesis with 80% and 90% power.

Change in Tumor Size. Among 20 patients treated with mAb therapy, the mean SD of the change in the sum of index lesions was 6 mm (15.8 mm). Using the SD and their 95% confidence intervals for qRT-PCR (predictor; data provided above) and change in tumor size among 29 patients, table 2 lists the true slope estimates that provide 80% power to reject the null hypothesis of no association between qRT-PCR and tumor response. Given our preliminary data, 29 patients provide 80% power to detect ( $p<0.05$ ) a 3.8 mm change in tumor volume per deltaCt cycle.

Table 14. True slope estimates (mm/cycle) required to achieve 80% power to reject the null hypothesis of no association between baseline qRT-PCR and change in the sum of index lesions.

SD for qRT-PCR	SD for Change in Tumor Size at Best Response		
	12	16	24
1.85	3.08	4.11	6.16

2	2.85	3.80	5.70
2.14	2.66	3.55	5.33

Patients from this protocol will also provide tissue for modelling individual gene expression (e.g., log(FPKM) using RNA-seq. Following extensive processing and quality control, we will model individual gene expression (e.g., log(FPKM) separately against  $^{11}\text{C}$ -Glutamine and  $^{18}\text{F}$ -FSPG PET as continuous dependent variables with standard linear regression with a FDR selection criteria of 5%. This gene signature will be confirmed using feature selection via the elastic net with 4-fold cross validation. This gene signature will be further annotated using knowledge base pathway analysis. Due to the relatively smaller sample size, we will further summarize the gene signature by generating a compound score based on the univariate regression analysis considering one gene at a time on change in tumor size (pFDR < 0.05) as a cutoff point for selection of important features. For the  $i^{\text{th}}$  patient, the compound score (prediction index) for the gene signature is:

$$c_i = \sum_{j=1}^k (\text{sign of } \beta_j) w_j x_{j,i} .^{52}$$

Here  $w_j$  is the Wald statistic and  $\beta_j$  is the coefficient from linear regression analysis for the set of  $j=1$  to  $k$  selected significant features. These summary prediction indices will again be used to predict change in tumor size. For that analysis, we will determine the statistical significance of the compound score using a permutation test (10,000 permutations). Further, we will carry out the same method using the Cox (proportional hazards) regression model (i.e.,  $h_i(t) = h_0(t) \exp(\psi c_i)$ ) for PFS. Finally, we will conduct internal validation and model calibration using Efron's optimism bootstrap ( $b=500$ ). Standard goodness-of-fit parameters (e.g. coefficient of determination) will be adjusted for over-optimism and predicted values adjusted to evaluate calibration plots that elucidate the predictive power of the gene expression model in future datasets.

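### The stated power of the qRT-PCR gene analysis holds only for one gene named in advance at an unadjusted 5% level; no gene is named and no error control is stated for this platform

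*Combined protocol and SAP*

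**What the plan says.** The glutamine-metabolism gene signature, using qRT-PCR and RNA-Seq, is a phase II secondary endpoint (Section 3.2).

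Under Gene expression signatures in Section 15, pre-treatment tissue is to be used for "qRT-PCR analysis of genes that regulate intracellular Gln metabolism". The hypothesis is that "qRT-PCR based gene expression is associated with change in tumor size, progression-free (PFS) and overall survival (OS"). Neither the number of genes nor any individual gene is given.

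The Power Analysis that follows takes the predictor's SD from preliminary data: the average SD "for the deltaCt values of 84 genes was 2 cycles (1.85 to 2.14 cycles"). With 29 patients it claims at least 90% power at hazard ratios of 1.35 (PFS) and 1.42 (OS), with 29 and 21 events expected by 12 months. For tumour size, "29 patients provide 80% power to detect ( $p<0.05$ ) a 3.8 mm change" per deltaCt cycle (Table 14). The caption of Figure 6 also uses p<0.05.

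The RNA-seq text comes next. Expression is modelled against PET uptake "with standard linear regression with a FDR selection criteria of 5"%. Genes are then selected one at a time on tumour-size change at pFDR < 0.05. They are combined into a compound score, which is tested with 10,000 permutations, carried into a Cox model for PFS and validated by bootstrap. All of this is introduced for RNA-seq with log(FPKM) as the measure. OS does not appear in it.

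**The concern.** Every effect in the qRT-PCR power text is per deltaCt cycle, and the SD of 2 is an average over individual genes. The unit of analysis is therefore one gene, not a score. The hypothesis, however, concerns a set of genes and three outcomes. A 5% level per gene is a 5% error rate only if one gene is chosen beforehand. If the set is screened, the number of chance findings grows with its size. If the screen is controlled, power at the stated effects is lower than stated.

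The section cannot be taken as purely descriptive. For radiotracer pharmacokinetics and for exosomes the plan says that no formal hypothesis tests will be done. For gene expression it states a hypothesis, a significance level and power. At stake is which genes are reported as linked to outcome in 29 patients.

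**Working it through.** **Inputs (Section 15).** Patients n = 29; events D = 29 (PFS) and 21 (OS); medians 1.9 and 6.4 months; predictor SD = 2; HR 1.35 and 1.42; slope 3.8 mm per cycle; tumour-change SD 16 (15.8 in the text). The PET time-to-event paragraph gives "a type I error of 5% and 80% or 90% power" and a two-sided alternative. I carry that sidedness over to qRT-PCR.

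**Step 1: reproduce the stated figures.**

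- Events, 29 × (1 − 0.5^(12/median)): 28.6 for PFS and 21.1 for OS (stated 29 and 21).
- Cox, one continuous predictor, power = Φ(√D × SD × ln HR − z):
  - PFS: √29 × 2 × ln 1.35 = 3.232; 3.232 − 1.960 = 1.272; power 89.8%.
  - OS: √21 × 2 × ln 1.42 = 3.214; 3.214 − 1.960 = 1.254; power 89.5%.
- Slope, r = 3.8 × 2/16 = 0.475; noncentrality 0.475/√(1 − 0.475²) × √29 = 2.907; noncentral t on 27 df, power 80.0%. All nine cells of Table 14 give 79.9% to 80.1%.

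The stated figures are thus single-gene power at unadjusted two-sided 0.05.

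**Step 2: false positives if m null genes are each tested at 0.05.** The trial's m is not stated, so it is an assumption here, ranged up to the preliminary count of 84. The expected number per outcome is 0.05m. The chance of at least one, with independent genes, is 1 − 0.95^m.

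**Step 3: power at the stated effects under Bonferroni within an outcome.** The formulas are those of Step 1 at level 0.05/m. For m = 84 the level is 0.000595 and z = 3.434, so PFS is Φ(3.232 − 3.434) = 42%.

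| m | Expected false positives per outcome | Chance of at least one | Power PFS / OS / tumour size |
|---|---|---|---|
| 10 | 0.5 | 40% | 66 / 66 / 46% |
| 20 | 1 | 64% | 58 / 58 / 36% |
| 40 | 2 | 87% | 50 / 49 / 28% |
| 84 | 4.2 | 99% | 42 / 41 / 20% |

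**Step 4: correlated genes.** In a simulation of 84 equally correlated null genes (40,000 runs), the chance of at least one false positive is 92%, 74%, 47% and 21% at correlations of 0.3, 0.5, 0.7 and 0.9. The expected count stays at 4.2.

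**Step 5: Benjamini-Hochberg at 5% over 84 independent genes** (20,000 runs), with every true gene at the stated effect:

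| True genes | PFS / OS / tumour size |
|---|---|
| 1 | 43 / 42 / 21% |
| 10 | 64 / 63 / 37% |
| 20 | 74 / 73 / 49% |
| 42 | 82 / 82 / 64% |

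**Step 6: effects detectable at 0.05/84.** HR 1.55 (PFS) and 1.67 (OS) for 90% power, and 5.3 mm per cycle for 80% power, against the stated 1.35, 1.42 and 3.8.

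**The case against.** The strongest reply is that the plan has no uncontrolled test to object to. The p<0.05 appears only in power statements and a figure caption, and no decision rule for qRT-PCR is written. The figure of 84 is the source of an SD estimate, not the trial's panel. The endpoint is one signature drawn from both platforms, so the authors may have meant the RNA-seq controls to govern both. Those controls are substantial and reach tumour size and PFS. The analysis is correlative and meant to give mechanistic insight.

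Much of this stands. A reader might infer that 84 genes will each be tested at an unadjusted 0.05 on three outcomes, so that false findings are near certain. The documents do not support that. They give neither the panel size nor such a rule, and the 99% figure needs 84 independent null genes, whereas genes from one pathway may well be correlated. A reader might also infer that the stated power collapses under any error control. That too goes too far: the lowest figures are Bonferroni, and under FDR control with half of 84 genes truly associated PFS and OS keep about 82%.

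What the reply does not remove is the gap. The control steps are not extended to qRT-PCR and omit OS on any reading. If they were meant to apply, the power was computed at the wrong level. Either way the text needs correcting.

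**Conclusion.** The concern holds as a gap in specification with a power statement that does not match the hypothesis. The stated 90/90/80% applies to one gene chosen in advance, and none is named. For several genes, power at the stated effects is lower in every scenario examined: from 66/66/46% (Bonferroni, 10 genes) to 42/41/20% (Bonferroni, 84 genes), and from about 43/42/21% to 82/82/64% under Benjamini-Hochberg over 84 genes.

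These figures rest on an assumed panel size. The Benjamini-Hochberg figures also rest on independent genes and on every true gene having the stated effect. The chance of a false positive depends strongly on correlation among genes; the expected number does not. The matter should be settled before the gene data are examined. It is confined to a secondary correlative endpoint and does not touch the Simon two-stage decision on response rate.

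**What to change.** In Section 15, under Gene expression signatures:

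1. State the number of genes on the qRT-PCR panel and list them.
2. Apply the 5% FDR rule already used for RNA-seq to the qRT-PCR genes, separately within tumour-size change, PFS and OS.
3. Label the hazard-ratio power statements, Figure 6 and Table 14 as single-gene, unadjusted power. Beside them give power at the adjusted level for the stated panel, with the assumed number of truly associated genes.

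The cost is a change of wording and less favourable stated power. No further patients, samples or data are needed.
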